## 2.2 Previous Data

**Middle-aged adults are quite interested in modified sports fitness program.** In two primary care practices in Central Pennsylvania in 2015, we anonymously surveyed 540 patients in the office before their visit. The response rate was 90.0% and most (59.6%) of adults 50 years of age or younger were interested in the program, which was described as “a regular fitness program where people your own age played games, such as softball, floor hockey and soccer, that were made to be easier to play and less competitive”. After adjusting for potential confounders, female patients and those with hypertension, high cholesterol or obesity were no less interested in participating [61].

**A pilot study in 2016 observed that the activities are moderate-vigorous and enjoyable.** We designed PlayFit in 2015 after observing the popularity of Pickleball—a version of tennis modified to reduce effort, with a smaller court and plastic ball [62]. Using this model, we settled upon a design for a physical activity program that consisted of five modified sports, all of which could be rotated in order to provide variety and minimize overuse injuries. We first recruited 14 adults for pilot studies in which we modified 10 commonly-played sports to reduce effort (e.g., smaller court, lightweight volleyball for soccer) and to maximize positive playful social interactions (e.g., choosing sides randomly each session, switching players if scores became lop-sided, minimizing physical contact and insisting that all players must touch the ball to score).

**In 2016, 22 adults participated in PlayFit for 3 months.** Five sports (e.g., kickball) were removed due to inadequate energy expenditure, leaving 5 (soccer, ultimate Frisbee, ultimate football, team handball and netball) that have a similar set of rules and, based on accelerometry, at least 88% of time was in the moderate-vigorous range and 24% in the vigorous range. Satisfaction, measured after each session using the Net Promoter Score [9], was high (7.7-8.4 out of 10). The comments were quite positive, including: “Oh my gosh, I’m sweating buckets!! That’s the best part, aside from the required rule to pass to all players-Yay teamwork!”, “It was really fun. There were enough rules to make sense but not enough to take away from the leisure activity”, and “Game was really fun. There was a great amount of teamwork needed with this game” (see PlayFit Comments table above). This positive social experience appears similar to the results of Band Together [63], a social strength training program that our team designed, now being studied in a 2100-person, PCORI-funded, clinical trial.

## 2.3 Study Rationale

**Study Design.** We propose a 12-month randomized trial to answer the following question for both patients, health care providers and fitness center directors: “What group exercise program will best promote long-term adherence and fitness?” The design consists of two activity conditions (Group Fitness, PlayFit). We hypothesize that, by enhancing perceived enjoyment and thereby attendance and adherence, PlayFit will lead to greater gains in fitness, and better physical and mental health than a traditional Group Fitness program. This study is built upon prior work showing that while low PA levels greatly increase risk of diseases such as CVD [41] and that increasing PA significantly reduces risk for several chronic conditions [43], fewer than 10% of adults actually meet PA guidelines [64, 65]. As perceived enjoyment consistently predicts adherence [10, 37], the overall body of evidence raises the question, not yet studied: “If adults are offered access to an exercise program designed to maximize enjoyment, would adherence and fitness increase?” The dominant models for PA promotion focus on enhancing motivation via goal-setting, tracking progress, providing feedback, and overcoming barriers to physical activity [7, 66]. The question to be answered in this study is complementary to that line of work, but expands the range of potential influences to include type of the physical activities themselves (designed to be enjoyable forms of “play” vs. not). As group fitness programs include “group” activities, we have included a Group Fitness condition to control for the effect of exercising in a group setting.

Group Fitness activities, however, do not typically include much interaction between participants. PlayFit, in contrast, includes a more intensive social interaction by focusing on team-based gameplay, yet designed to reduce competitiveness and maximize enjoyment. In most group fitness classes, social interaction is optional and the activities are not typically designed to be inherently enjoyable. PlayFit, by comparison, requires social interaction and taps into a powerful source of enjoyment - play. A worldwide survey by the furniture company IKEA observed that physical play was rated, by children, as more enjoyable than even television or video games [67]. Despite the importance of play to the human experience, few adults play sports [49] and few studies noted in meta-analyses of physical activity have applied aspects of play to adult physical activity promotion [68].

**What could occur if PlayFit outperforms Group Fitness classes?** We believe that three things would occur. First, fitness centers would offer programs such as PlayFit, in order to maximize social engagement, which fitness centers already use to help members make new friends which help people maintain their membership longer [69]. PlayFit is designed to be used on a basketball court, which is present in many fitness centers. We would make the protocol publicly available, in the public domain for free, to encourage its use. Second, it may lay the foundation for changing advice to patients from providers. Rather than focusing simply on the amount of activity and intensity of activity, providers could encourage patients to focus on how enjoyable the activity is to their patients. Third, it may lay the foundation for a change in exercise prescriptions to include a focus on enjoyment. At the present time, exercise prescriptions focus on frequency, intensity, type (moderate v. vigorous) and time (duration) [70]. Fourth, the design elements adapted for PlayFit—modifying where the intervention takes place, targeting whom the intervention takes place with, and altering what is done during the intervention—could be applied to other preventive health behaviors, such as healthy eating, to further refine interventions [42, 71-74].

**Can PlayFit improve physical activity across the lifespan and in among groups with specific barriers to physical activity?** We propose conducting a feasibility study (which we refer to in this document as “Feasibility Study”) to understand whether PlayFit is feasible for groups of people who may also benefit from increasing physical activity, but who are not part of the RCT of PlayFit versus Group Fitness. The rationale for these specific groups is as follows. First, older adults have the most to gain from physical activity but are the least active, so modifying PlayFit for this population has the potential to improve population health. Second, the greatest decline in physical activity during life is between ages 8-11 and ages 11-14, where there is a 75% decline in minutes of activity [38], making this a critical period for

intervening to enhance physical activity. Third, while exercise has been proven repeatedly to improve mental health outcomes in patients with major depressive disorder (MDD), those patients have unique barriers to performing new activities that often make them unwilling to start a physical activity program, despite how much it may help them. To answer those questions we will enroll up to 150 participants, up to 50 adolescents ages 10-12 and in the 6th or 7th grade, up to 50 adults age 51-70 and up to 50 adults currently being treated for major depressive disorder. Adults of each group will be invited to participate in a focus group, to inform changes to PlayFit to adapt it to the specific target population. All 50 of each group will then be given access to the modified version of PlayFit, to be held several times each week for 3 months.

## 3.0 Inclusion and Exclusion Criteria

### 3.1 Inclusion Criteria

#### Focus Groups

- Age 21+.
- Sedentary, defined as less than 90 minutes of moderate or vigorous activity each week.

#### Feasibility Study:

- Age 10-12 and in the 6th or 7th grade for Adolescent Feasibility Study
- Age 51-70 for Older Adult Feasibility Study.
- Age 18+ being treated (medicines or talk therapy, as in Mental Health History Measure) for major depressive disorder (MDD) and with at least mild levels of depression (score of  $\geq 8$ ), as measured by the Hamilton Rating of Depression (HAM-D), for Major Depression Feasibility Study
- For the Major Depressive Disorder feasibility study, all participants will be required to be categorized as Sedentary, defined as less than 90 minutes of moderate or vigorous activity each week. This will be determined using Physical Activity items from the National Health Interview Survey [75].
- For the Older Adult feasibility study, all participants will be required to be categorized as Sedentary, defined as less than 60 minutes of moderate or vigorous activity each week. This will be determined using Physical Activity items from the National Health Interview Survey [75].
- For the Adolescent feasibility study, all participants will be required to be categorized as Sedentary, defined as less than 60 minutes of moderate or vigorous activity each day. This will be determined using Physical Activity items from the National Health Interview Survey [75].

#### RCT

- Age 18-50.
- Sedentary, defined as less than 90 minutes of moderate or vigorous activity each week. This will be determined using Physical Activity items from the National Health Interview Survey[75].
- Must have access to the Internet at home.

### 3.2 Exclusion Criteria

#### Focus Groups

- Potential subjects who cannot read and speak English.
- Health care provider told subject they had a heart condition and should only do physical activity recommended by a doctor.

## Feasibility Study

- Physician, Nurse Practitioner or Physician's Assistant is unwilling to sign permission for subjects with between 2 and 4 risk factors for heart disease, of the following 5 (sedentary lifestyle, smoking, high blood pressure, high cholesterol, early heart disease in a family member), or unwilling to sign permission for potential subjects who disclose any of the following COVID-19-specific items during screening (family member with current or past COVID-19 infection, moderate-to-severe asthma, takes medication for or has a medical condition that weakens the immune system, symptoms of COVID-19 infection).
- A history of Heart disease, diabetes, angina, heart failure, stroke, mini-stroke (transient ischemic attack), weak or failing kidneys
- Symptoms of chest pain, dizziness, loss of consciousness, a bone or joint problem that can be worsened with physical activity or being diagnosed with a heart condition by a doctor, based on questions from the Physical Activity Readiness Questionnaire (PAR-Q) [76]
- Inability to read and speak English.
- Pregnant or planning to become pregnant in the next four (4) months.
- Planning to have surgery or move in the next four (4) months.
- Suicidality, schizophrenia, psychosis or bipolar disease, among subjects in the feasibility study for subjects with major depressive disorder (MDD), based on a affirmative response (>0) to question 3 on the Hamilton Rating Scale for Depression (HAM-D) [27].

## RCT

- Physician, Nurse Practitioner or Physician's Assistant is unwilling to sign permission for subjects with between 2 and 4 risk factors for heart disease, of the following 5 (sedentary lifestyle, smoking, high blood pressure, high cholesterol, early heart disease in a family member), or unwilling to sign permission for potential subjects who disclose any of the following COVID-19-specific items during screening (family member with current or past COVID-19 infection, moderate-to-severe asthma, takes medication for or has a medical condition that weakens the immune system, symptoms of COVID-19 infection). The same rule will apply to household members, who will need the same permission from a health care provider if 2, 3, or 4 cardiac risk factors are present.
- A history of Heart disease, diabetes, angina, heart failure, stroke, mini-stroke (transient ischemic attack), weak or failing kidneys
- Symptoms of chest pain, dizziness, loss of consciousness, a bone or joint problem that can be worsened with physical activity or being diagnosed with a heart condition by a doctor, based on questions from the Physical Activity Readiness Questionnaire (PAR-Q) [76]
- Four or more risk factors for coronary artery disease, of those listed above (sedentary lifestyle, smoking, high blood pressure, high cholesterol, early heart disease in a family member).
- Age over 50.
- Participating in another research project involving physical activity or weight loss.
- Planning to have surgery or move in the next year.
- Potential subjects who cannot read and speak English.
- Pregnant or planning to become pregnant in the next year
- If blood pressure at the Baseline Visit is > 160 systolic OR >100 diastolic OR heart rate is > 120 bpm, research staff will suggest the individual to see a PCP to control their blood pressure or heart rate, and if they would like to still participate in our study they can be tested again in the future.
- Unwilling to wear a face covering during the mandate period (COVID-19).

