**Secondary Objectives:** AIM 3: Test the feasibility (FEASIBILITY STUDY) of PlayFit to enhance physical activity levels among children age 10-12 and in the 6th or 7th grade, adults age 51-70 and adults being treated for major depressive disorder. We hypothesize that access to PlayFit 3-5 times weekly for 3 months will increase MVPA levels (versus baseline) for all participants and that objective measures of perceived enjoyment will be associated with attendance.

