## 4.0 Recruitment Methods

### 4.1 Identification of subjects

We will send letters to patients of the Penn State Health, who reside in the zip codes of interest. Mailing lists will be generated by EIM. Patients age 18-50 who reside in a 10 mile radius around the exercise sites will be sent a letter. We, too, will generate mailing lists by EIM for recruitment of patients aged 51-70 years old. We will also place advertisements in newspapers, Facebook pages and communications from township park departments, schools or other community messaging print medium. We will also post printed advertisements (i.e., flyers) in public spaces frequented by potential participants. We will also use radio advertisements and advertisements when callers are on hold with the phone system phone system at Penn State Hershey. Of note, there is no specific maximum age, but participants to date in the pilot work have been under 50 years of age. If older participants hear about the study, they will be screened and treated the same as those who respond to a letter and are younger. For focus groups, participants in our prior research projects of PlayFit, who have previously given us permission to contact them for future studies, may also be called by phone to seek their participation.

We will also mail to potential subjects using a third-party list from a marketing company, such as Lorton Data, limited to those that live nearby the exercise site. When possible we will partner with community organizations that can send IRB-approved recruitment letters to members of their community, such as to parents of school students in the case of the Middletown Area Recreation Alliance.

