#### Feasibility – Adolescent, Major Depressive

The feasibility study is designed in two phases, among two separate populations (adolescents age 10-12 and in the 6th or 7th grade, adults being treated for major depressive disorder). First, we will conduct focus groups among adults to identify changes to the PlayFit intervention that will be needed to adapt it to the target population. Second, we will conduct a 2-month single-group study among 50 members of each group to understand the rate of attendance and whether exposure to PlayFit increases the level of physical activity (using an activity monitor worn at baseline, and monthly for 2 months) and perceived enjoyment from physical activity.

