#### Feasibility – Older Adult

The feasibility study is designed in two phases, among adults 51-70. First, we will conduct focus groups among adults to identify changes to the PlayFit intervention that will be needed to adapt it to the target population. Second, we will conduct a 3-month single-group study among 50 members to understand the rate of attendance and whether exposure to PlayFit increases fitness (measured by V02 at the baseline and 12-week time points) as well as the level of physical activity (using an activity monitor worn at baseline and the 12-week time point) and perceived enjoyment from physical activity.

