#### Feasibility Studies: Older Adult

All participants will be in the study for approximately 3 months, including a one-time focus group and then the 3 months of PlayFit participation, which will start approximately one month later.

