## **8.0 Subject Numbers and Statistical Plan**

### **8.1 Number of Subjects**

Focus Groups:

We will enroll 100 subjects

RCT:

We will enroll up to 470 subjects.

Feasibility Studies:

We will enroll up to 50 subjects in each of the three studies, or up to 150 total. We hypothesize that access to PlayFit will increase the minutes of moderate-vigorous PA from 10 minutes per day (SD=20) at baseline to 20 minutes per day (SD=30) after 3 months. As there is a dose-response relationship between MVPA and mortality, a doubling of MVPA should be expected to lead to a 60% reduction in mortality [41]. To achieve 80% power for these differences (with an alpha of <0.05), we will enroll up to 50 subjects at baseline, anticipating losses to follow-up of no more than 8 (16%) after 8 weeks, leaving up to 42 for analysis.

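### The feasibility exclusions omit the RCT's bar on concurrent activity or weight-loss research, although these single-group studies judge MVPA only against the participant's own baseline

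*Combined protocol and SAP*

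**What the plan says.** **RCT exclusions (3.2).** The list bars people "Participating in another research project involving physical activity or weight loss".

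**Feasibility exclusions (3.2).** The list shares the cardiac, symptom, language, pregnancy and surgery items. Its time windows are cut from one year to four months, for example "Planning to have surgery or move in the next four (4) months". It has no item on other activity or weight-loss research.

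**Design (7.1).** For adolescents and adults with major depression: "we will conduct a 2-month single-group study among 50 members of each group". For older adults: "we will conduct a 3-month single-group study among 50 members". Neither has a comparator.

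**Hypothesis (1.1, Aim 3).** Access to PlayFit "will increase MVPA levels (versus baseline) for all participants". Accelerometer MVPA is the main outcome in both feasibility schedules in 7.2.

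**Entry rule (3.1).** Participants must be sedentary: under 60 minutes of MVPA a week (older adults), under 90 minutes a week (depression), or under 60 minutes a day (adolescents).

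**Ages (3.1).** RCT 18-50; depression study 18 and over; Older Adult study 51-70.

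**Former PlayFit participants (4.1).** On focus-group recruitment, the section says that "participants in our prior research projects of PlayFit, who have previously given us permission to contact them for future studies, may also be called". Section 7.3 describes Older Adult participation as "including a one-time focus group and then the 3 months of PlayFit participation".

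**The concern.** The exclusion is present where randomisation would in any case tend to balance outside programs between arms, and absent where nothing balances them. In a before-after design, minutes gained in another program between baseline and follow-up go straight into the estimated PlayFit effect.

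The analysis cannot remove them. The feasibility schedules in 7.2 contain no item on other exercise programs, the self-report activity questionnaire (IPAQ) is listed for the RCT only, and a waist accelerometer does not show which program produced the minutes.

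The protocol's own studies also overlap. An adult of 18-50 treated for depression can fit both the RCT and the depression study. One of 51-70 can fit both the depression and Older Adult studies. RCT household members receive an exercise program too. The RCT item, applied when someone enters the RCT, does not stop that person from joining a feasibility study later; only an item on the feasibility list would. At stake is whether the Aim 3 change in MVPA can be read as PlayFit's, and whether a Group Fitness participant could receive PlayFit by a side door.

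**Working it through.** **1. The two lists side by side.** The pregnancy and surgery/move items were carried over with shorter windows, so the RCT and feasibility lists were aligned item by item to some degree. The concurrent-research item was not carried over, and no reason is given.

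**2. What the sedentary rule covers.** Per day, the limits are 60/7 = 8.6 min (older adults), 90/7 = 12.9 min (depression) and 60 min (adolescents). A program worth 10 min/day is 70 min/week. Already under way at screening, it would alone breach the Older Adult limit, would use 70 of the 90 minutes allowed in the depression study, and would pass easily in the adolescent study. Such a program is also in the baseline accelerometer reading, so at constant intensity it cancels in the change. What remains is a program that starts or steps up after baseline.

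**3. The plan's own feasibility figure (8.1).** The hypothesis is to "increase the minutes of moderate-vigorous PA from 10 minutes per day (SD=20) at baseline to 20 minutes per day (SD=30) after 3 months", with 80% power, alpha 0.05, 50 enrolled and 8 lost.
- Dropout: 8/50 = 16%, and 42/(1 - 0.16) = 50. This agrees.
- SD of change = sqrt(20² + 30² - 2·rho·20·30) = sqrt(1300 - 1200·rho). The correlation rho is not stated, so the 42 cannot be reproduced from the text alone. Assuming a two-sided paired t-test, 80% power at n = 42 needs rho of about 0.66 and an SD of change of about 22.6. At rho = 0.5 the SD is 26.5 and power at 42 is 67%.

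**4. Size of the bias.** The documents give neither a co-enrolment rate nor a gain from other programs, so these inputs are assumptions: k of the 42 analysed gain 10 min/day from a program begun after baseline.

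Bias in the mean change = 10 × k/42.

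| k of 42 | Bias (min/day) | Share of planned 10 | False increase, SD 22.6 | False increase, SD 26.5 |
|---|---|---|---|---|
| 0 | 0 | 0% | 2.5% | 2.5% |
| 4 | 0.95 | 10% | 4.5% | 4.2% |
| 8 | 1.90 | 19% | 7.7% | 6.6% |

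The last two columns give the chance of a significant rise when PlayFit itself adds nothing (noncentral t, 41 df, upper tail of a two-sided 5% test). The unstated correlation matters little here.

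**5. A wider range.** With rho = 0.65 (SD 22.8) and both tails counted, 10% of participants gaining 20 min/day shifts the mean by 2 min/day (chance of significance 9%). With 20% gaining 20 it is 4 min/day (20%). With 30% gaining 30 it is 9 min/day (71%). Co-enrolment would have to be common, and the outside programs strong, to produce the whole hypothesised gain.

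**The case against.** **The sedentary rule already does most of the work.** This stands for activity under way at screening in the Older Adult and depression studies. It does not stand for adolescents, for programs begun later, or for a weight-loss study with little activity at entry.

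**The item would not make the gain attributable to PlayFit.** This stands. It covers research projects only, so gym or community programs remain allowed. Regression to the mean after selecting sedentary people, season and reactivity to the monitor also remain. That limits the benefit of the change but does not argue for leaving the gap.

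**These are small feasibility studies with attendance as a stated purpose, and broad eligibility is partly a preference.** This is fair, and it keeps the point minor.

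**A stronger reading concerns earlier PlayFit.** A reader might infer from 4.1 and 7.3 that former participants are recalled through the focus groups into the PlayFit phase, and that their earlier exposure produces the MVPA gain. The documents support neither step. Section 4.1 names former participants for focus groups only, and no section says that they continue. Section 7.3 says feasibility participants attend a focus group, not that every focus-group member joins a feasibility study. PlayFit completed before baseline is part of the baseline value and does not itself create a rise from it. What is left is selection: people already known to like the program could raise attendance and enjoyment, which Aim 3 links. That supports recording earlier exposure. A blanket exclusion would go beyond the RCT list.

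**Conclusion.** The omission is real: the feasibility list lacks an exclusion that the RCT list has, in studies whose only contrast is before versus after. It leaves open a research program begun or stepped up after baseline, and concurrent enrolment in this protocol's own overlapping studies. The documents do not show that either has occurred.

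The consequence is modest and its true size is unknown. Under the assumption of 4 or 8 of 42 gaining 10 min/day elsewhere after baseline, the mean change is inflated by about 1 or 2 min/day. The planned RCT comparison and all stated sample sizes stand as they are, unless RCT participants actually cross into a feasibility study. This is a cheap improvement and not a flaw that undermines the studies.

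**What to change.** 1. In 3.2, add the RCT's concurrent-research item to the feasibility exclusions. State that it includes concurrent enrolment in the PlayFit RCT (also as a household member) or in another PlayFit feasibility study.
2. At feasibility screening, record any earlier PlayFit exposure, and report attendance and enjoyment with and without those participants.
3. Optionally, ask at each follow-up about other exercise or weight-loss programs, since the copied item does not reach non-research programs. Report the MVPA change as descriptive.

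Cost: one or two screening questions and a slightly smaller recruitment pool, plus one follow-up question if item 3 is taken up. The 50 enrolled and 42 analysed per study do not change.
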